#### c. Kansas City Cardiomyopathy Questionnaire (KCCQ)

KCCQ scores at baseline and 1 year will be quantified as continuous variables ranging from 0 to 100 and the difference between the two time points will be calculated. This difference (i.e., delta) will be analyzed with paired T statistic with a two-sided alpha of 0.05. The null (H0) and alternative (H1) hypotheses are:

 $H_0: \Delta_{Device} = \Delta_{Control}$  $H_1: \Delta_{Device} \neq \Delta_{Control}$ 

 $\Delta_{\text{Device}}$  and  $\Delta_{\text{Control}}$  represent mean deltas for the Device and Control groups, respectively.

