9.2 One Hundred Eighty (180) Day Follow-Up Evaluation

An evaluation will be scheduled for 180 day follow-up (± 14 days). The following assessments will be performed:

- Medical History
- NYHA Class
- Cardiovascular Medications
- Targeted Physical Exam
- 12-lead ECG
- Transthoracic Echocardiography
- Complete blood count (no WBC differential necessary)
- Chemistry panel
- NT-Pro-BNP or BNP
- Kansas City Cardiomyopathy Questionnaire (KCCQ)
- SF-36v2 Health Survey (SF-36)
- 6 Minute Walk Test (6MWT)
- Neurological Assessments

Neurological Assessments will be conducted by a neurologist, a neurology fellow, or designee. Every effort should be made to have a neurologist or neurology fellow perform the neurological assessments, or alternatively, a trained research team member certified in stroke assessments, which consist of:

- NIHSS
- Modified Rankin Scale (mRS): mRS can be obtained by a certified research team member via phone interview with the patient or caregiver member if the patient is unable to visit the research office.
- Continued Activity Monitoring data collection from baseline to the 180 day follow-up.
 - At the 180 day follow-up visit, the patient will return the Activity Monitoring Devices.
 If a patient's daily wear compliance rate (minimum 8 hours between 6am to 10pm) is
 less than 50% in the 30 days prior to the visit, an additional month (30 days) of Activity
 Monitoring will be completed. Devices will be returned following the month of Activity
 Monitoring.
- Adverse Events

PROTOCOL NUMBER: 2017-05

If the patient reports any adverse events that are potentially serious during the follow-up period, the patient should return to the investigator's facility for further evaluation of the event.

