13.4.4 Key Secondary Endpoints (through 1 year)

The following secondary efficacy endpoints will be tested in a hierarchical order after the primary endpoints have passed (i.e., achieved statistical significance at pre-specified alpha level), in order to address multiple testing and control family-wise error. When one of the endpoints does not achieve statistical significance at two-sided alpha = 0.05

PROTOCOL NUMBER: 2017-05

in favor of the Device group, no further testing of subsequent endpoints will be conducted.

Mitral Regurgitation (MR)

Superiority test of Device group versus Control group via the chi-square statistic, for the difference in the prevalence of MR \leq 1+ at one year, with a two-sided alpha of 0.05. The null (H_0) and alternative (H_A) hypotheses are:

 H_0 : $P_{CardB} - P_{Control} = 0$

 H_A : $P_{CardB} - P_{Control} \neq 0$.

 P_{CardB} and $P_{Control}$ are the prevalence of MR \leq 1+ at one year in the Device and Control groups, respectively.

New York Health Association (NYHA)

Superiority test of Device group versus Control group via the Chi-square statistic, for the difference in the proportion of subjects with NYHA class I/II at one year, with a twosided alpha of 0.05. The null (H_0) and alternative (H_A) hypotheses are:

 H_0 : $P_{CardB} - P_{Control} = 0$

H_A: P_{CardB} - P_{Control} ≠ 0.

P_{CardB} and P_{Control} are the proportion of subjects with NYHA I/II at one year in the Device and Control groups, respectively. Fisher's Exact Test will be performed if assumptions for the Chi-square test are not met.

Kansas City Cardiomyopathy Questionnaire (KCCQ)

The KCCQ scores at baseline and 1 year will be quantified as continuous variables ranging from 0 to 100 and the difference between the two time points will be calculated. This difference (i.e., delta) will be analyzed with T statistic with a two-sided alpha of 0.05. The null (H_0) and alternative (H_A) hypotheses are:

 H_0 : $\Delta_{CardB} = \Delta_{Control}$

HA: ∆CardB ≠ ∆Control

PROTOCOL NUMBER: 2017-05

 Δ_{CardB} and $\Delta_{Control}$ represent mean deltas for the Device and Control groups, respectively.

Six Minute Walk Test (6MWT)

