### 8.4 Key Secondary Efficacy Endpoints (1 Year)

Secondary efficacy endpoints will be tested in hierarchical order after the primary endpoints to address multiplicity and preserve alpha at the .05 level. When one of the endpoints does not achieve statistical significance in favor of the Device group, no further testing of subsequent endpoints will be conducted.

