#### d. Six Minute Walk Test (6MWT)

The 6MWT distance at baseline and 1 year will be quantified as continuous variables measured in meters and the difference between the two time points will be calculated. This difference in distance (i.e., delta) will be analyzed with paired T statistic with a two-sided alpha of 0.05. The null ( $H_0$ ) and alternative ( $H_1$ ) hypotheses are:

H0:  $\Delta_{\text{Device}} = \Delta_{\text{Control}}$ H1:  $\Delta_{\text{Device}} \neq \Delta_{\text{Control}}$ 

 $\Delta_{Device}$  and  $\Delta_{Control}$  represent mean deltas for the Device and Control groups, respectively.

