#### e. SF-36v2 Health Survey (SF-36)

SF-36 score at baseline and 1 year will be quantified as continuous variables ranging from 0 to 100 and the difference between the two time points will be calculated. This difference (i.e., delta) will be analyzed with paired T statistic with a two-sided alpha of 0.05. The null (H0) and alternative (H1) hypotheses are:

H0:  $\Delta_{\text{Device}} = \Delta_{\text{Control}}$ H1:  $\Delta_{\text{Device}} \neq \Delta_{\text{Control}}$ 

 $\Delta_{\text{Device}}$  and  $\Delta_{\text{Control}}$  represent mean deltas for the Device and Control groups, respectively.

THIS DOCUMENT CONTAINS CONFIDENTIAL AND PROPRIETARY INFORMATION OF EDWARDS LIFESCIENCES, LLC. IT MUST NOT BE REPRODUCED OR DISCLOSED TO THIRD PARTIES WITHOUT PRIOR WRITTEN PERMISSION OF EDWARDS LIFESCIENCES, LLC. (This template is required by DOC

	2017-05 Sta	tistical Analysis Plan I			1.0   7/16/20	19
$\mathbb{P}$	Revision Date: Febr	uary 28, 2019	Rev		For Use Only by Affiliates of Edwards Lifesciences	Page 15 of 18
Edwards	Title	Statistical Analysis Plan for ACTIVE 2017-05				

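### KCCQ, 6MWT and SF-36 are tested on unadjusted change from baseline; adjusting for the baseline value would be more precise at almost no cost

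*SAP*

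**What the plan says.** SAP 8.4c states for KCCQ that "the difference between the two time points will be calculated", and then: "This difference (i.e., delta) will be analyzed with paired T statistic with a two-sided alpha of 0.05". SAP 8.4d has the matching sentence for 6MWT: "This difference in distance (i.e., delta) will be analyzed with paired T statistic with a two-sided alpha of 0.05". SAP 8.4e treats SF-36 the same way, starting from "SF-36 score at baseline and 1 year will be quantified as continuous variables ranging from 0 to 100". Protocol 13.4.4 describes the same change scores but calls the test a T statistic, without the word paired. In all three cases the null hypothesis is that mean change is equal in Device and Control.

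No covariate is named. SAP 6.1 allows covariate analyses as an option but specifies none, although Protocol 13.4.1 says the SAP will pre-specify them. The rank-sum fallback for non-normal data in SAP 6.1 is also unadjusted. Patients without the visit leave the denominator (SAP 6.1), and nothing is imputed (SAP 6.2).

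All three measures are also taken at 30 and 180 days (Protocol 9.1 and 9.2), but the 1-year tests do not use those values.

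The sequence rule in SAP 8.4 is: "When one of the endpoints does not achieve statistical significance in favor of the Device group, no further testing of subsequent endpoints will be conducted". Heart failure hospitalization, cardiovascular death and all-cause mortality follow SF-36.

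**The concern.** Subtracting baseline fixes its coefficient at 1. If the true regression slope of the 1-year score on baseline is below 1, the change score keeps baseline noise that an estimated slope would remove. The comparison then has a larger standard error than the collected data require.

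A miss on any one of the three tests closes the rest of the sequence. The protocol (5.4) and SAP (3.6) both label these endpoints as powered, yet neither gives an SD, correlation, mean effect or power for any of the three mean-change tests. The margin therefore cannot be read from the plan.

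**Working it through.** **Inputs from the documents.** There are 375 patients, allocated 2:1. SAP 8.11 expects data on 60% for co-primary endpoint 1 (225 patients, 150:75) and allows 20% dropout for co-primary endpoint 2 (300 patients, 200:100). It assumes 20% one-year mortality in both arms, and 10% Control versus 50% Device responders on both KCCQ (10 points or more) and 6MWT (40 m or more). Entry 6MWT is 150 to 400 m.

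**The plan's own figure.** None exists for these three tests. The nearest is power above 99% for co-primary endpoint 1 (10% versus 70%). At 150:75 the null SE is √(0.25 × (1/75 + 1/150)) = 0.0707 and the alternative SE is √(0.09/75 + 0.21/150) = 0.0510. Then (0.60 − 1.96 × 0.0707)/0.0510 ≈ 9.0, so the stated power is reproduced.

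**Variance ratio.** Let s0 and s1 be the baseline and 1-year SDs and rho their correlation.
- Change score: s0² + s1² − 2·rho·s0·s1.
- Baseline-adjusted: s1²(1 − rho²).
- With s0 = s1, the ratio is (1 − rho²)/(2(1 − rho)) = (1 + rho)/2.

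The documents do not give rho, so a range is shown. The third column is 1/ratio − 1. The last is Φ((1.96 + 0.84)/√ratio − 1.96).

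| rho (assumed) | Adjusted / change variance | Extra patients the change score needs | 80% power becomes |
|---|---|---|---|
| 0.3 | 0.65 | 54% | 93.5% |
| 0.5 | 0.75 | 33% | 89.9% |
| 0.7 | 0.85 | 18% | 86.0% |

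The 80% starting point is illustrative and is not a figure from the plan. A simulation of 4,000 trials at 150:75 gave ratios of 0.747 (rho 0.5) and 0.854 (rho 0.7). With a true effect of 0.30 SD, both estimators averaged between 0.300 and 0.302, so neither is biased.

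**6MWT.** The entry range limits the baseline spread: a flat distribution over 150 to 400 m has SD 250/√12 = 72 m. Assume baseline SD 65 to 72 m, 1-year SD 80 to 100 m and rho 0.4 to 0.6.
- Largest gain (72, 80, 0.4): 6400 × 0.84 / (5184 + 6400 − 4608) = 5376/6976 = 0.77.
- Smallest gain (65, 100, 0.6): 10000 × 0.64 / (4225 + 10000 − 7800) = 6400/6425 = 0.996.

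In the second case the slope rho·s1/s0 is 0.92. A slope near 1 leaves almost nothing to gain.

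**Power at the planned effect.** For normal change scores with equal SDs, 10% versus 50% responders implies a shift of 1.28 SD of change. At 150:75 the SE is √(1/75 + 1/150) = 0.141 SD. The noncentrality is 1.28/0.141 = 9.1, so power exceeds 99.9% before any adjustment. The smallest effect detectable with 80% power is 2.80 × 0.141 = 0.40 SD of change at 225 patients and 0.34 SD at 300. Adjustment matters for effects of about that size.

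**The 30- and 180-day scores.** Let R² be the share of residual 1-year variance that they explain (assumed 0.25 to 0.50). A repeated-measures model multiplies the variance by 1 − R²(1 − observed/alive). If 80% of 375 (300) survive and 225 have a 1-year score, the factor is 1 − 0.25 × 0.25 = 0.94 to 1 − 0.50 × 0.25 = 0.875. If every survivor has a 1-year score, the factor is 1.

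**The case against.** The strongest reply is that this is a preference about efficiency. A reader might infer that the change-score tests are biased or invalid, or that chance baseline imbalance is a further harm. The documents do not support that: the trial is randomised, the contrast is unbiased in complete data and keeps its alpha, and variation from chance imbalance is already in its standard error. This part of the reply stands.

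The reply also holds that the planned KCCQ and 6MWT effects leave nothing to rescue. That is right if those effects occur. But they are planning assumptions, and SF-36 has none.

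A reader might infer that lost power here costs every later endpoint. The plan assumes identical all-cause (20%) and cardiovascular (15%) mortality in the two arms, so there is no planned effect to lose on either. For heart failure hospitalization, taking five or more as five, the assumed means are 1.05 and 0.80. A simple comparison of mean counts at 200:100 has about 27% power, though this only approximates the planned recurrent-event model. The sequence protects little planned power, but a narrow miss on SF-36 would still prevent that test from being made.

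A reader might also infer that a repeated-measures model on all visits is free. With 20% mortality assumed and no rule for deaths, it would implicitly model scores after death and change what is estimated.

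Finally, the paired t wording might suggest that only within-group tests will be run. The stated hypotheses compare the two arms, and SAP 6.1 uses paired for patients with both measurements, so a mismatch of wording is the safer reading.

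**Conclusion.** The point holds as a recommended improvement in precision; it does not show a validity error. The direction is certain: the adjusted variance does not exceed the change-score variance, and is below it unless the slope on baseline is 1. The size is not certain, because it rests on SDs and correlations that the documents do not give. For KCCQ and SF-36 with equal SDs, a reduction of 15% to 35% is plausible at rho 0.7 to 0.3. For 6MWT the reduction runs from 23% to 0.4%. The practical consequence is confined to true effects well below the planned ones, and to SF-36.

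Separately, the SAP's test name does not fit its own hypothesis and differs from the protocol. SAP 10 does not list that difference among the changes from the protocol.

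**What to change.** In SAP 8.4c-e and Protocol 13.4.4, replace the test with a between-group ANCOVA of the 1-year value on treatment, baseline value and ischemic/non-ischemic stratum (a randomisation factor), and test the treatment coefficient at two-sided 0.05. Keep the order and the stopping rule. State whether the SAP 6.1 rank-sum fallback still applies to these endpoints, because it would bring back an unadjusted comparison. Record the change in SAP 10, and make it before any unblinded results are seen.

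This takes wording and standard programming, with no new data or patients. It does not recover survivors who lack a 1-year score. A repeated-measures model using the 30- and 180-day values could do so and is optional, but it needs a pre-stated rule for deaths.

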#### d. Six Minute Walk Test (6MWT)

The 6MWT distance at baseline and 1 year will be quantified as continuous variables measured in meters and the difference between the two time points will be calculated. This difference in distance (i.e., delta) will be analyzed with paired T statistic with a two-sided alpha of 0.05. The null ( $H_0$ ) and alternative ( $H_1$ ) hypotheses are:

H0:  $\Delta_{\text{Device}} = \Delta_{\text{Control}}$ H1:  $\Delta_{\text{Device}} \neq \Delta_{\text{Control}}$ 

 $\Delta_{Device}$  and  $\Delta_{Control}$  represent mean deltas for the Device and Control groups, respectively.

#### e. SF-36v2 Health Survey (SF-36)

SF-36 score at baseline and 1 year will be quantified as continuous variables ranging from 0 to 100 and the difference between the two time points will be calculated. This difference (i.e., delta) will be analyzed with paired T statistic with a two-sided alpha of 0.05. The null (H0) and alternative (H1) hypotheses are:

H0:  $\Delta_{\text{Device}} = \Delta_{\text{Control}}$ H1:  $\Delta_{\text{Device}} \neq \Delta_{\text{Control}}$ 

 $\Delta_{\text{Device}}$  and  $\Delta_{\text{Control}}$  represent mean deltas for the Device and Control groups, respectively.

THIS DOCUMENT CONTAINS CONFIDENTIAL AND PROPRIETARY INFORMATION OF EDWARDS LIFESCIENCES, LLC. IT MUST NOT BE REPRODUCED OR DISCLOSED TO THIRD PARTIES WITHOUT PRIOR WRITTEN PERMISSION OF EDWARDS LIFESCIENCES, LLC. (This template is required by DOC

	2017-05 Sta	tistical Analysis Plan I			1.0   7/16/20	19
$\mathbb{P}$	Revision Date: Febr	uary 28, 2019	Rev		For Use Only by Affiliates of Edwards Lifesciences	Page 15 of 18
Edwards	Title	Statistical Analysis Plan for ACTIVE 2017-05				

### f. Heart Failure Hospitalizations

The number of heart failure hospitalizations between day 0 and day 365 post procedure will be quantified as recurrent events and analyzed with a survival analysis intensity model (Andersen and Gill, 1982). The null ( $H_0$ ) and alternative ( $H_1$ ) hypotheses are:

H0: HR = 1 H1: HR ≠ 1

HR represents hazard rate for Device group relative to Control group. A two-sided alpha of 0.05 will be used.

### g. Cardiovascular Mortality

Cardiovascular mortality rate up to 365 days will be compared between the Device and Control groups using time-to-event analysis and log-rank test. The null ( $H_0$ ) and alternative ( $H_1$ ) hypotheses are:

 $H_0: HR = 1$  $H_1: HR \neq 1$ 

HR represents hazard rate for Device group relative to Control group. A two-sided alpha of 0.05 will be used.

#### h. All-Cause Mortality

All-cause mortality rate up to 365 days will be compared between the Device and Control groups using time-to-event analysis and log-rank test. The null ( $H_0$ ) and alternative ( $H_1$ ) hypotheses are:

H₀: HR = 1 H₁: HR ≠ 1

HR represents hazard rate for Device group relative to Control group. A two-sided alpha of 0.05 will be used.

### 8.5 Additional Secondary Endpoints (1 Year)

Additional secondary endpoints: technical, device, procedural, and patient success, and responder analysis will be compared between Device and Control groups and descriptively summarized with patient counts, percentages, and confidence intervals.

### 8.6 Key Echocardiography Endpoints (5 Years)

Descriptive statistics for key echocardiography endpoints will be compared between Device and Control groups.

### 8.7 Long Term Outcomes (5 Years)

Descriptive statistics for long term outcomes will be compared between Device and Control groups.

### 8.8 Long Term Safety Outcomes (5 Years)

Descriptive statistics for long term safety outcomes will be compared between Device and Control groups.

THIS DOCUMENT CONTAINS CONFIDENTIAL AND PROPRIETARY INFORMATION OF EDWARDS LIFESCIENCES, LLC. IT MUST NOT BE REPRODUCED OR DISCLOSED TO THIRD PARTIES WITHOUT PRIOR WRITTEN PERMISSION OF EDWARDS LIFESCIENCES, LLC. (This template is required by DOC.))

### 2017-05 Statistical Analysis Plan | VV-TMF-259558 | 1.0 | 7/16/2019

Edwards	Revision Date: February 28, 2019		Rev		For Use Only by Affiliates of Edwards Lifesciences	Page 16 of 18
	Title	Statistical Analysis Plan for ACTIVE 2017-05				

### 8.9 Adherence and Retention

Adherence to protocol requirements and patient dispositions will be summarized by treatment.

### 8.10 Interim Analysis

The sample size will be re-estimated when at least 40% of patients have undergone 1 year primary efficacy endpoint assessment. This re-estimated will be conducted through simulation in the following steps:

- a. Data from the sample that has completed the study will be treated as fixed and retained in each simulation
- b. Data from patients who have not completed the study will be simulated, under the assumption that the observed data in the sample from (a) is representative of the true population value for the four co-primary endpoints 2 (see section 3.2.2).
- c. Data from (a) and (b) will be combined and the Finkelstein-Schoenfeld methodology will be conducted and resulting probability will be calculated.
- d. Steps (a) through (c) will be repeated 10,000 times.
- e. The proportion of the 10,000 iterations for which the resulting probability from the Finkelstein-Schoenfeld test is less than .05, will be taken as the estimate of conditional power.

If the conditional power is < 90% than the sample size will be re-estimated to include the number of patients necessary to achieve 90% conditional power. The group allocation ratio of 2:1 (Device vs Control) will be retained. Increase in the sample size will be at the discretion of the sponsor and pursuant to FDA approval. Additional scenarios (e.g., conditional power is < 80%) may be requested.

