If the conditional power is <90% then the sample size will be reestimated to include the number of patients necessary to achieve 90% conditional power. The group allocation ratio of 2:1 (Device vs. Control) will be retained. Increase in the sample size will be at the discretion of the Sponsor and pursuant to FDA approval. Additional scenarios (such as 80% power) may be requested.

All event rates above are conservative estimates based on previous experience with the Edwards Cardioband System, as well as on data on patients with functional mitral regurgitation who underwent catheter based treatment with the CE marked CARILLON® device (Cardiac Dimensions, Kirkland, WA) or the MitraClip® device (Abbott Vascular, Santa Clara, CA) from two registries (Sentinel¹ and ACCESS-EU²) and three studies (EVEREST II³,4, TRAMI⁵-7, TITAN®).

Clinical Events	A group of individuals with pertinent expertise that reviews clinical study
Committee (CEC)	endpoints to determine whether the endpoints meet protocol-specified
	criteria.
Data Safety	An independent data monitoring committee that may be established by
Monitoring Board:	the sponsor to assess, at intervals, the progress of a clinical trial, the
	safety data, and the critical efficacy endpoints, and to recommend to the
	sponsor whether to continue, modify, or stop a trial.

Table 1: Schedule of Study Visits and Patient Assessments

Test/ Assessment	Screening/ Baseline	Random -ization	Pre-Index Procedure- Edwards Cardioband System (Device group only; timing: per local institutional standard of care)	Index Procedure- Edwards Cardioband System (Device group only)	Post- Edwards Cardioband System Procedure, Pre- Discharge (Device group only)	30 Day F/U (±7 days)	180 Day F/U (± 14 days)	1 Year F/U (±45 days)	2 Year F/U (± 60 days)	3, 4, 5 Year F/U (± 60 days)
Study Visit No.	1	2	3	4	5	6	7	8	9	10, 11, 12
Study Consent	X									
Medical Hx/	Х					X	Х	Х	Х	Х
NYHA Class										
STS Score	Х									
Cardiovascular	Х			Х	Х	Х	Х	Х	Х	X
Medications										
Targeted	Х					Х	Х	Х	Х	Х
Physical Exam										
12-Lead ECG	Х				X	Х	Х	Х		
Transthoracic	Х				Х	Х	X	X	Х	Х
Echo (TTE)										
Transesophageal	Х			Х						
Echo (TEE)	X									
Cardiac CT	X									
Imaging Randomization		X								
Pregnancy Test	X ¹	^	X							
(for females of	^-		Χ							
childbearing										
potential only)										
potential only)	 	 								

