#### 2.3 Randomization and Blinding

Randomization is ideally performed within seven days prior to the scheduled procedure, but no more than 14 days prior. If a patient is randomized to Control, the scheduled interventional case is cancelled and the patient is notified that they have been enrolled in the Control/medical therapy arm of the trial and will not need to undergo an interventional procedure. The process of randomizing after a case is scheduled has been implemented to ensure that the time frame between randomization and actual treatment is minimized. Eligible patients will be randomly assigned in a 2:1 ratio to either Device group or Control group, respectively.

Randomization schedule will be generated using the Balance module in Medidata RAVE, the Electronic Data Capture System for the study. Randomization will be stratified by (a) site and (b) baseline ischemic vs non-ischemic disease. This randomization schedule will be masked to patients, site personnel, study team, and sponsor as defined in the Randomization and Blinding Plan. Only the unblinded statistician and designates will be privy to the masked randomization scheme.

All analyses of data by the study statistician/programmer will be conducted blinded to treatment assignment (similar to the conduct of blinded clinical study to the extent possible), until the time of database lock for the primary endpoint analysis. Analyses of unblinded data such as DSMB analysis will be performed by a separate non-study or independent statistician/SAS programmer.

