### 8. STATISTICAL ANALYSIS OF STUDY ENDPOINTS

### 8.1 Co-Primary Hypothesis 1

H0:  $P_{Device}(T=1) - P_{Control}(T=1) = 0$ H1:  $P_{Device}(T=1) - P_{Control}(T=1) \neq 0$ 

where

H₀	= Null hypothesis
H1	= Alternative hypothesis
P Device	= Proportion of patients in the Device group with $MR \le 2+$ at 1 year
P Control	= Proportion of patients in the Control group with MR $\leq$ 2+ at 1 year
Т	= Time (years)

The co-primary hypothesis 1 tests the superiority in reducing MR of the Device group relative to the Control group via Chi-Square test for two independent proportions with two-sided alpha = .05. Co-primary efficacy endpoint 1 must meet statistical significance in order to proceed to co-primary efficacy endpoints 2. This approach does not require any adjustment for multiplicity.

### 8.2 Co-Primary Hypothesis 2

 $H_0$ : None of the four co-primary endpoints 2 are improved by treatment  $H_1$ : At least one of the four co-primary endpoints 2 is improved by treatment

- i. Time to all-cause death within the first year
- ii. Number of heart failure hospitalizations within the first year
- iii. Improvement in Six Minute Walk Test (6MWT) at 1 year relative to baseline (≥ 40 meters improvement)
- iv. Improvement in Kansas City Cardiomyopathy Questionnaire (KCCQ) at 1 year relative to baseline (≥ 10 points improvement)

The co-primary hypothesis 2 tests the superiority of the Device group relative to the Control group for the hierarchical sequence of the four co-primary endpoints 2 via the Finkelstein-Schoenfeld test (Finkelstein and Schoenfeld, 1999). The Finkelstein-Schoenfeld test is a generalization of the Gehan Wilcoxon test. Each patient pair is compared in descending order of the endpoints until one member of the pair shows superiority. While the example comparison given in the table below shows a Device patient being compared to a Control patient it should be noted that a pairwise comparison is made for every patient in Device group versus every patient in Control group.

THIS DOCUMENT CONTAINS CONFIDENTIAL AND PROPRIETARY INFORMATION OF EDWARDS LIFESCIENCES, LLC. IT MUST NOT BE REPRODUCED OR DISCLOSED TO THIRD PARTIES WITHOUT PRIOR WRITTEN PERMISSION OF EDWARDS LIFESCIENCES, LLC. (This template is required by DOC.))

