The Finkelstein-Schoenfeld method is a simple non-parametric statistical test for analyzing the impact of treatment which combines multiple events (e.g., death and hospitalizations) with longitudinal measures of clinical effect (e.g., 6MWT and KCCQ). The test is based on a Wilcoxon rank sum test. We define a score,  $\mu_{ij}$ , which is chosen to reflect whether patient i has had the more favorable outcome than patient j by following the hierarchy of scoring provided in table 1. If one of the patients has the more favorable outcome, his score is +1 and the other patient has a score of -1. If it is not possible to assign either patient as having the better outcome, then both patients get a score of 0.

This is a score test based on the sum of scores for the Device group. Suppose there are N total patients in the trial, let  $D_i = 1$  for patients in Device group and  $D_i = 0$  for patients in the Control group. Using the  $\mu_{ij}$  for every pair of patients defined above, we assign a score to each patient,  $U_i = \sum_{i \neq j} \mu_{ij}$ . The test is now based on

$$T = \sum_{i=1}^{N} U_i D_i.$$

Finkestein and Schoenfeld refers to this test as the generalization of the Gehan Wilcoxon (GGW) test. The null hypothesis is that none of the endpoints in table 1 are different between Device and Control group. The alternative hypothesis is that at least one endpoint in table 1 is different between Device and group.

Let m be the number of patients in the Device group. The mean of T is zero and its variance is

$$V = \frac{m(N-m)}{N(N-1)} (\sum U_i^2).$$

The hypothesis of interest is tested by comparing  $L = \frac{T}{\sqrt{V}}$  to the normal distribution. Hence, we are looking for a z-score that is indicative of a significant difference (p < .05) between the Device and Control groups.

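### The sample-size re-estimation in SAP 8.10 has no conditional-power floor and the final Finkelstein-Schoenfeld test is unadjusted, so the two-sided 0.05 for co-primary endpoint II is not guaranteed

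*SAP*

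**What the plan says.** SAP 8.10 re-estimates the sample size once at least 40% of patients have had their 1-year primary efficacy assessment. Completed patients are kept as they are. The rest are simulated "under the assumption that the observed data in the sample from (a) is representative of the true population value" for the four components of co-primary endpoint II. The Finkelstein-Schoenfeld (FS) test is run on the combined data 10,000 times, and conditional power is the share of runs in which "the resulting probability from the Finkelstein-Schoenfeld test is less than .05". The trigger follows: "If the conditional power is < 90% than the sample size will be re-estimated to include the number of patients necessary" to reach 90%. On who decides, the SAP says: "Increase in the sample size will be at the discretion of the sponsor and pursuant to FDA approval". The Protocol synopsis (Sample Size & Endpoint Analysis) has the same trigger and the same condition: "Increase in the sample size will be at the discretion of the Sponsor and pursuant to FDA approval".

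For the final analysis, SAP 8.2 takes L = T/√V over all patients and refers it to the normal distribution: "we are looking for a z-score that is indicative of a significant difference (p < .05". Both documents state a two-sided alpha of 0.05 for this test. Its only gate is in SAP 8.1: "Co-primary efficacy endpoint 1 must meet statistical significance in order to proceed to co-primary efficacy endpoints 2". The remark there that no multiplicity adjustment is needed concerns that testing order, not the re-estimation. Protocol 13.1 and 13.4.9 leave the interim method to the SAP.

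**The concern.** SAP 8.10 does not use the word unblinded, but an FS test on observed data needs the treatment labels, so the sample size is changed using the comparative result. Any conditional power below 90%, however low, can lead to a larger trial. Step (e) counts every p below .05, so a trend towards Control also qualifies as written. The interim may fall anywhere from 40% onwards.

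When the sample grows after a poor first stage, the pooled statistic gives that stage less weight than planned. If the treatment has no effect, this raises the chance of crossing 1.96. Nothing in SAP 8.2 compensates.

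Co-primary endpoint II carries the clinical-benefit claim and must succeed before any key secondary endpoint is tested. Because it is tested only after co-primary endpoint I, the error matters most when the device lowers MR without improving outcomes. That is exactly the case in which co-primary endpoint I gives almost no protection.

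**Working it through.** **Inputs from the documents.** Two-sided alpha 0.05 (critical value 1.96), 2:1 allocation, 375 enrolled giving 300 evaluable (200 Device, 100 Control), interim at information fraction t of 0.40 or later, current-trend conditional power, 90% target, conventional final test. **Assumed, because the documents do not say:** a maximum of 1.5, 2 or 3 times the planned size, or none; looks at 40%, 50% and 60%; every permitted increase is made.

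**Model.** Let z be the interim statistic and I the final information (1 = as planned).
- Conditional power in Device's favour: CP(z, I) = Φ{[z√t + (z/√t)(I − t) − 1.96√I] / √(I − t)}.
- If CP(z, 1) < 0.90, I rises until CP = 0.90 or the cap is reached.
- Null chance of a Device-favouring rejection given z: 1 − Φ{[1.96√I − z√t] / √(I − t)}.
- Type I error is this probability, with its Control-tail counterpart, integrated over a standard normal z.

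**The plan's own figure.** With I fixed at 1 the integral gives 0.025 per tail and 0.0500 two-sided, as stated.

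**How the inflation arises (t = 0.40).** At z = 0.5, CP is 6.6%. The null rejection probability is 1 − Φ[(1.960 − 0.316)/0.775] = 0.017 at the planned size and 1 − Φ[(2.772 − 0.316)/1.265] = 0.026 at twice that size. At z = 1.5, CP is 70%. The rule asks for 1.69 times the size, and the probability falls from 0.096 to 0.080. Increases at low conditional power inflate the error; increases at high conditional power reduce it.

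**Rule as written, conventional test.** Columns are the assumed caps. The first three rows show Device tail / two-sided; the last three show two-sided only.

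| Increase made on | t | 1.5x | 2x | 3x | none |
|---|---|---|---|---|---|
| Device trend only | 0.40 | 0.0262 / 0.0525 | 0.0267 / 0.0540 | 0.0271 / 0.0556 | 0.0276 / 0.0588 |
| Device trend only | 0.50 | 0.0268 / 0.0528 | 0.0275 / 0.0545 | 0.0281 / 0.0564 | 0.0287 / 0.0604 |
| Device trend only | 0.60 | 0.0274 / 0.0531 | 0.0284 / 0.0549 | 0.0291 / 0.0571 | 0.0300 / 0.0619 |
| Either direction | 0.40 | 0.0550 | 0.0580 | 0.0613 | 0.0676 |
| Either direction | 0.50 | 0.0556 | 0.0590 | 0.0628 | 0.0708 |
| Either direction | 0.60 | 0.0562 | 0.0599 | 0.0642 | 0.0738 |

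For either-direction increases at t = 0.40, each tail is 0.0275 to 0.0338.

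**Check with the FS statistic itself.** 60,000 null trials per setting used the SAP control-arm rates in both groups (20% mortality, the listed hospitalization distribution, 10% 6MWT and 10% KCCQ responders), independent components, complete follow-up and an interim at 120 of 300.
- Device trend only: Device tail 0.0262 (2x) and 0.0260 (3x); two-sided 0.0526 and 0.0533.
- Either direction: two-sided 0.0585 (2x) and 0.0611 (3x).
- Monte Carlo standard error: about 0.0007 per tail and 0.001 two-sided.

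A separate, smaller simulation (6,000 and 4,000 trials) gave 0.058 and 0.061 for either-direction increases, against 0.047 and 0.049 with the size held fixed.

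**The co-primary I gate.** The chance of passing in Device's favour is Φ{(pD − pC − 1.96·s0)/s1}, where s0 and s1 are the pooled and unpooled standard errors. At 20% against 10%: s0 = √(0.1667 × 0.8333 × 0.015) = 0.0456, s1 = √(0.16/200 + 0.09/100) = 0.0412, giving Φ(0.26) = 0.60. With no MR effect it is 0.025, and at 30% against 10% it is 0.99. The plan assumes 70% against 10%.

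**With a Device-favouring conditional-power floor, conventional test, all four caps (two-sided).**

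| Floor | t = 0.40 | t = 0.50 | t = 0.60 |
|---|---|---|---|
| 30% | 0.0491–0.0494 | 0.0484–0.0490 | 0.0476–0.0485 |
| 50% | 0.0491–0.0493 | 0.0486–0.0489 | 0.0481–0.0485 |

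A 10% floor at t = 0.40 gives 0.0502 to 0.0509.

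**The case against.** The strongest reply is that the error that matters is small. Only a Device-favouring rejection supports the device. At the 40% look with increases on Device trends, that tail exceeds 0.025 by 0.0012 to 0.0026, and more than half of the two-sided excess lies in the Control tail. In the FS simulation the Device tails of 0.0262 and 0.0260 are within two standard errors of 0.025, so that setting alone does not clearly show inflation. This stands as a statement about size. It does not restore the stated level: the integration exceeds 0.05 under every cap, and the Device tail grows at the later looks that SAP 8.10 leaves open.

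The largest figures need the trial to be enlarged on a Control-favouring trend, and 0.068 also needs unlimited size. A threefold cap already means 3 × 375 = 1,125 patients. They are best read as bounds on what the text allows.

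Sponsor discretion, FDA approval and the Protocol 15.1 approval process for significant changes are real review points, but none sets a limit that controls the error. The 375 and 600 patient totals describe the initial plan and are not caps after re-estimation. SAP 2.3 says "Analyses of unblinded data such as DSMB analysis will be performed by a separate non-study or independent statistician/SAS programmer"; that protects trial conduct, not the significance level.

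A 10% floor would hold the Device tail at 0.0242 to 0.0248, so it fails only against the two-sided 0.05. That is nevertheless the level the plan states.

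**Conclusion.** The point holds. SAP 8.10 permits increases driven by the observed effect at any conditional power below 90%. SAP 8.2 keeps the unadjusted FS test, and neither document supplies anything that preserves 0.05. At a 40% look, two-sided error is about 0.053 to 0.059 if only Device-favouring trends lead to an increase and 0.055 to 0.068 if either direction does. At 60%, the Device tail reaches 0.0274 to 0.0300 on Device trends only. These sizes rest on the assumed caps, on every permitted increase being made, and on the normal approximation, which the FS simulation supports for the two-sided error at 40%. The inflation is modest, but it affects the claim of clinical benefit and should be removed before the interim.

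**What to change.** Amend SAP 8.10 before the interim, choosing one of two routes.

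- **Conditional-power floor.** Fix the interim fraction. Define conditional power as the share of runs with FS p < .05 and T > 0. Allow an increase only when it is at or above a stated floor and below 90%. Keep the conventional FS test. Floors of 30% and 50% both hold 0.05 at looks of 40% to 60%, whatever the cap.
- **Fixed weights.** Keep the present rule, but test co-primary endpoint II with √0.4·z1 + √0.6·z2 (for a 40% look), where z1 is the FS statistic from the interim cohort and z2 that from all other patients. This gives 0.05 by construction if the stages are independent (simulated 0.052 and 0.0525, standard error about 0.003). The interim cohort must therefore be defined by randomization order, not by who has completed the study, because an early death could otherwise decide membership.

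A stated maximum sample size is advisable for feasibility but does not by itself control the error. The independent statistician is already in place.

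**Cost.** The floor rules out some increases. If the design assumptions hold and power is 87% to 90% (SAP 8.11 says 87%, the Protocol synopsis above 90%), conditional power at a 40% look falls below 30% in about 14% to 17% of trials and below 50% in 21% to 24%. For 87% power and a 30% floor: Φ[0.983 − (1.960 + 1.126)√0.4] = 0.166. Fixed weights lose a little efficiency, because later patients are under-weighted and pairs across stages are not compared. Otherwise the change is a few SAP sentences.
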